5.3 EXCLUSION CRITERIA

1. Threshold blood pressure of 80/40 mmHg-- patients with both a systolic blood pressure of less than 80 mmHg and a diastolic blood pressure of less than 40 mmHg.
2. Irreversible brain damage based on available historical and clinical information.
3. Patients with a solid organ transplant or those with a bone marrow or stem cell transplant in the previous 100 days or who have not engrafted.
4. Acute or chronic use of circulatory support device, other than ECMO, such as LVADs, RVADs, BIVADs.
5. Presence of preexisting advanced chronic renal failure (i.e., ESRD) requiring chronic renal replacement therapy prior to this episode of acute kidney injury or with pre-existing chronic kidney disease (CKD) defined as a eGFR <30 ml/min/1.73m 2 . Patients who have never seen a pediatric nephrologist will be assumed not to have pre-existing CKD.
6. AKI occurring in the setting of burns, obstructive uropathy, vasculitis, scleroderma renal crisis, atheroembolism, functional or surgical nephrectomy, cyclosporine or tacrolimus nephrotoxicity.
7. Received >12 hour of CRRT (not including SCUF on ECMO) during this hospital admission or prior to transfer from an outside hospital.
8. Received >1 hemodialysis treatment during this hospital admission or prior to transfer from an outside hospital.
9. Metastatic malignancy which is actively being treated or may be treated by chemotherapy or radiation during the subsequent three month period after study therapy.
10. Chronic immunosuppression with the exception of corticosteroids up to a dose of 10 mg per day.
11. HIV or AIDS.
12. Severe chronic liver failure as determined by standard diagnostic requirements.

13. Current Do not Attempt Resuscitation (DNAR), Allow Natural Death (AND), or withdrawal of care status, or anticipated change in status within the next 7 days.
14. Patient not expected to survive 28 days because of an irreversible medical condition. (This is not restrictive to AKI, and may include situations such as the presence of irreversible brain damage, untreatable malignancy, inoperable life threatening condition, or any condition to which therapy is regarded as futile by the PI.)
15. Any medical condition that the Investigator thinks may interfere with the study objectives.
16. Physician refusal.
17. Dry weight <15 kg.
18. Platelet count <15,000/mm³.

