6.2 CRRT PARAMETERS

6.2.1 CITRATE ANTICOAGULATION

Each participating clinical site will use their regional citrate anticoagulation protocol. The clinical site is responsible to achieve, and maintain a serum post filter ionized calcium level of <0.40 mmol/L throughout the entire observation period (day and night). The serum post filter ionized calcium level will be collected from the CRRT Circuit post SCD [REDACTED]

To alleviate the metabolic derangements associated with regional citrate based anticoagulation:

- a) *Alkalosis:* Patients with an arterial pH <7.40 at enrollment will initiate CRRT with solutions containing either 25 or 35 meq/L

of base as directed by local standard of care. During the study, if the patient's arterial pH increases to >7.45 OR the patient's serum bicarbonate increases to >35 meq/L, the CRRT solution will be changed to a base concentration of 25 meq/L, OR 0.9% NaCl will be added dialysis fluid to correct the alkalosis per local standard of care.

b) *Citrate lock:* If the patient develops citrate lock, as defined by a serum ionCa <0.95 mmol/L and a total serum Ca >12.5 meq/L, the citrate infusion will be discontinued OR the CRRT clearance will be increased by 50% per local standard of care, AND CRRT circuit Ca and patient Ca will be checked at least every one hour. For centers that stop citrate, once the patient ionCa is >1.0 mmol/L, the citrate will be restarted at 50% of the previous rate, and hourly ionCa pairs will be rechecked x 3 to ensure a stable patient ionCa >1 mmol/L and stable circuit ionCa <0.40 mmol/L.

Of importance the clinical plan is to monitor the perfusion circuit iCa levels at least q1h at the initiation of regional citrate anticoagulation (RCA) until a steady state iCa range is between 0.25 to 0.40 mmol/L. Once established, iCa levels both in the circuit and in the patient will be monitored q6h. If the iCa is outside the targeted range or alterations in citrate or calcium infusion rates are made, iCa levels are measured at least q1h until targeted ranges are once again achieved. Of importance, for efficacy of SCD treatment, iCa levels must be maintained in the recommended range at least 90% of the time, based on a sensitivity analysis showing that the mortality endpoint difference was lower with target iCa 80-85% of total treatment in clinical trial SCD-003.

The protocol example identified in **Appendix K** may be utilized.

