Besides the test of the hypothesis the study is focused on observable, empirical and laboratory determinations of patient safety while on the SCD. Previous human trials have been conducted on the SCD device and the protocol contains a review of AE and SAE data from all SCD human studies and findings from those studies contributed to constructing the investigative safety profile. Safety endpoint measures specified in the protocol include adverse events, laboratory safety parameters, vital signs, ventilation status and hemodynamic variables. Device integrity and performance measurements are also defined as are circumstances which demand premature termination of SCD treatment.

Prolonged exposure to the SCD is anticipated to result in superior outcomes, although as noted above, this pilot study is not designed to assess for efficacy. However, we understand that a minimum amount of exposure to the SCD will be required for an appropriate safety analysis and for making any inference regarding efficacy. The ppCRRT experience demonstrated that the majority of patients (201/370) received CRRT for 1 to 7 days and exhibited 65% survival (Symons et al CJASN 2007 Table7). Assuming our trial includes patients with similar illness severity, we have established a 72 minimum number of hours a patient will be treated with the SCD to be included in the final outcome analysis.

This trial is an early safety efficacy study but is not powered for statistical significance. Insights into a comparison of historical controls matched to SCD treated patients will utilize the ppCRRT Registry to match for: etiology of AKI, co-morbidities, CRRT modality, dose and form of anticoagulant, adverse events. [10].

The ppCRRT Registry has data fields for the primary reason for CRRT, including AKI and its cause, as well as co-morbidities which will be matched for primary organ system involvement. The CRRT modality was evenly distributed between convective and diffusive modality, with 60% of the convective modalities provided as CVVH and 40% as CVVHDF. The anticoagulant protocol will be standardized with ACD-A/CaCl₂ and all centers used the same protocol in ppCRRT Registry as outlined in this study protocol. Thus, the ppCRRT Registry dataset will be able to be matched to our study patient cohort. Also as noted above, patients will be matched for age, size and PRISM II score.

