APPENDIX E – CRRT MANAGEMENT

Continuous Renal Replacement will be provided to all patients enrolled in the SCD-PED-01 Trial using automated equipment with integrated ultrafiltration control.

CRRT Modality:	Continuous
Blood Flow Rate:	Prescribed by Investigator Team – Treating Team
Dialysate Type:	Prescribed by Investigator Team – Treating Team
Dialysate Rate:	Prescribed by Investigator Team – Treating Team
Replacement Fluid Type:	Prescribed by Investigator Team – Treating Team
Ultrafiltration:	Prescribed by Investigator Team – Treating Team
Anticoagulation:	Regional Citrate Anticoagulation Only
Anticoagulation Prescription:	Prescribed by Investigator Team – Treating Team
CRRT Device	Gambro PrismaFlex, B. Braun Diapact
Hemofilter:*	Gambro Prismaflex HF 1000, Renaflow HF 400, Renaflow HF 700, Renaflow HF 1200
CRRT System Change:	Per participating center protocol
SCD █ Change:	Every 24 hours and as needed due to clotting
SCD Blood Tubing Set Change	With each SCD change
CRRT+SCD Interruption:	Up to twelve (12) hours per 24 hour period (or up to 24 hours if interruption was needed to initiate ECMO in the middle of the SCD course)

*Hemofilters can be provided to site by sponsor upon request. The clinical site will agree to use one of the protocol approved hemofilters for therapy.

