 - i. 50 ml/hour as post-filter replacement fluid via the replacement fluid pump using (PrismaSolTM). This is necessary to prevent clotting of the deaeration chamber (50 ml/hour is the lowest allowable rate)
 - ii. The remaining fluid rate (total replacement fluid rate – 50 ml/hour) pre-filter replacement fluid via the pre-blood pump (PBP) using PrismaSolTM.
 - c. The composition of PrismaSateTM and PrismaSolTM should be equivalent. Any additives (e.g. potassium chloride) should be added in equivalent concentrations to both dialysis and replacement solutions.

3. Regional citrate anticoagulation: All CRRT circuits will receive regional citrate anticoagulation. The initial prescription and calcium level monitoring will be based on the size of patients and the presence, or lack thereof, of significant hepatic dysfunction. **REMEMBER TO ACCOUNT FOR THESE FLUIDS IN THE PATIENT REMOVAL RATE AS THESE ARE EXTERNAL TO THE CRRT MACHINE.**

a. Patients > 1 year of age and with normal hepatic function:

- i. Order ACD-A™ and CaCl₂ (8 grams/1 liter NS) to bedside
- ii. Initial ACD-A™ rate = 1.5 x CRRT blood pump rate x min/hour (e.g., if blood pump rate is 100 ml/minute; the ACD-A™ rate is 150 ml/hour). This is to be infused at a stopcock or y-connector on access line.
- iii. Initial CaCl₂ rate = 0.6 x blood pump rate x min/hour (e.g., if blood pump rate is 100 ml/minute; the CaCl₂ rate is 60 ml/hour).
- iv. Calcium monitoring schedule
 1. Check patient total and ionized calcium prior to CRRT initiation.
 2. Check patient and system ionized calcium 5 minutes after CRRT settings at prescribed rates.
 3. Check patient and system ionized calcium 2 hours after CRRT settings at prescribed rates.
 4. Check patient and system ionized calcium every 8 hours thereafter
 5. Check patient total calcium daily
 6. Check patient and system ionized calcium one hour after any change in ACD-A™ or CaCl₂ rate

b. Desired Calcium Concentration ranges

- i. Circuit ionized calcium = 0.25 to 0.40 mmol/L
- ii. Patient ionized calcium = 1.1 to 1.3 mmol/L (a higher level may be requested by ICU/CICU service if clinically indicated)
- iii. Patient systemic calcium = 8 to 12 mg/dL

c. Citrate anticoagulation management

- i. Bedside RN to call for patient ionCa < 1 mmol/L or > 1.5 mmol/L, or circuit ionCa < 0.25 mmol/L or > 0.40 mmol/L
- ii. Circuit ionCa managed with ACD-A™ rate
 1. For circuit ionCa < 0.25 mmol/L, decrease ACD-A™ 10%
 2. For circuit ionCa > 0.40 mmol/L, increase ACD-A™ 10%

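### Section 11 supports registry matching partly with a standardized ACD-A/CaCl₂ protocol that the operative sections leave to sites, and the Appendix K example checks calcium less often than the protocol requires

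*Combined protocol and SAP*

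**What the plan says.** Section 11 plans a comparison with historical controls from the ppCRRT registry and lists the factors to be matched, among them CRRT modality and the form of anticoagulant. It then says: "The anticoagulant protocol will be standardized with ACD-A/CaCl₂ and all centers used the same protocol in ppCRRT Registry as outlined in this study protocol". The next sentence concludes from this and the points before it that the registry can be matched to the trial cohort.

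The sections that instruct the sites read differently. Section 6.2.1 opens with "Each participating clinical site will use their regional citrate anticoagulation protocol" and offers Appendix K as an example that sites are free to use. Appendix E fixes the anticoagulant as "Regional Citrate Anticoagulation Only", but its row for the anticoagulation prescription says "Prescribed by Investigator Team – Treating Team". The ACD-A and CaCl₂ starting rates stand in item 3 of Appendix K (for ACD-A, "rate = 1.5 x CRRT blood pump rate x min/hour"), and that appendix is itself titled an example.

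On monitoring, Section 6.2.1 asks for hourly circuit iCa until steady state and then circuit and patient iCa every 6 hours. The Section 6.4 table and Appendix F repeat the 6-hourly rule for post-filter iCa, and Section 6.4 gives that measurement a window of 1 hour either way. Appendix K, item 3, sets patient and circuit checks every 8 hours after the 2-hour check.

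**The concern.** Registry controls are the comparator described for mortality and dialysis dependency. A reader of Section 11 would take it that trial and registry patients had the same citrate regimen, so that anticoagulation could be set aside as a source of difference. If the regimen varies by site, that reassurance is not available from the design.

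The monitoring conflict is practical. Section 6.2.1 says the device's efficacy depends on iCa being in range at least 90% of the time. A site that adopts the supplied example in good faith would follow a schedule that breaks the protocol's own rule.

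**Working it through.** There is no power, alpha or sample-size figure to reproduce, so the first check sets the texts side by side.

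| Element of anticoagulation | Binding on all sites? | Where |
|---|---|---|
| Regional citrate as the anticoagulant | Yes | Appendix E |
| Circuit iCa 0.25 to 0.40 mmol/L (below 0.40) | Yes | 6.2.1 |
| Hourly, then 6-hourly iCa checks | Yes | 6.2.1, 6.4, Appendix F |
| Handling of alkalosis and citrate lock | Yes, largely under local standard of care | 6.2.1 |
| Stopping SCD if the iCa target is not met within 12 hours of starting CRRT | Yes | 7.3, item 9 |
| Possible closure of a site that does not hold iCa below 0.40 mmol/L | Yes | 8 |
| Citrate product | No | Named in Section 11 and Appendix K only |
| Starting citrate and calcium infusion rates | No | Appendix K only |
| Titration steps | No | Appendix K only |

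Two rules touch on dosing without making a regimen. Section 6.2.1 has centers that stop citrate for citrate lock restart at 50% of the previous rate, and Appendix L asks for a calcium dose at the start in the smallest patients.

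The Section 11 sentence can be read in two ways. If it points to Appendix K, it points to something optional. If it points to Section 6.2.1, that section names neither ACD-A nor a starting rate. On neither reading do the operative sections require one ACD-A/CaCl₂ protocol.

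The second check is the monitoring interval.

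- Per 24 hours at uninterrupted steady state: 24/6 = 4 checks under 6.2.1, 6.4 and Appendix F; 24/8 = 3 under Appendix K.
- Over the 168-hour maximum, on the same assumption: 168/6 = 28 against 168/8 = 21, so 7 fewer, or 7/28 = 25%.
- Window: read as the time since the last check, the longest allowed gap is 6 + 1 = 7 hours, and 8 exceeds 7. Read as fixed clock times, windows of 1 hour either side of times 6 hours apart do not overlap, so three checks cannot fill four of them.

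The totals are illustrations, because Section 6.4 returns to hourly checks after any rate change or interruption and Appendix K adds its own checks at 5 minutes, at 2 hours and one hour after a rate change. The conflict between 8 and 6 hours does not depend on them.

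**The case against.** The strongest reply is that citrate is titrated to circuit iCa, and that target is binding, monitored and backed by stopping rules for patients and sites. The documents treat achieved iCa, not infusion rate, as what matters for the device. The words about standardizing could also be taken to name the agents only. Much of this stands: a shared target limits how far achieved anticoagulation can differ. But it supports a narrower statement than the one made. Even the agents are not required outside Section 11, and the sentence goes on to claim one protocol in common with the registry.

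The matching list also mentions dose. This may mean CRRT dose or anticoagulant dose. If the latter, regimen intensity is already to be matched; the text does not settle it, and the claim of a standardized protocol would still not fit Section 6.2.1.

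A reader might infer several stronger points that the documents do not support:

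- **That the comparison is biased, or that the registry statement is false.** The documents give no registry iCa or citrate-rate data. Registry practice cannot be checked here, and unverifiable is not the same as wrong.
- **That children with hepatic dysfunction have no regimen.** Appendix K prints rates only for "Patients > 1 year of age and with normal hepatic function", but it is optional. The site's own protocol governs, so no child is left without one.
- **That the later list of control factors in Section 11 drops anticoagulation.** That list is introduced as inclusive, not exhaustive, and does not replace the earlier one.
- **That an exact share of required checks would be missed over a course.** That needs unbroken steady state throughout, which rate changes, interruptions and restarts make unlikely.

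**Conclusion.** The point holds in a narrow form and is minor. Section 11 offers a standardized ACD-A/CaCl₂ protocol as one premise for registry matching, while Section 6.2.1 and Appendix E standardize citrate use, the iCa target, monitoring, and complication and stopping rules, and leave product, starting rates and titration to sites. Any effect on the historical comparison, which Section 11 says is not powered for statistical significance, is unknown and may be nil.

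The Appendix K interval is a plain inconsistency with the binding rule: 8 hours against 6, or three checks a day instead of four at steady state. It affects only sites that adopt the example as printed, and it is not evidence of bias. Both conclusions rest on the text alone and assume that Section 6.2.1 and Appendix E govern what sites do.

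**What to change.** 1. In Appendix K, item 3, change the routine patient and circuit iCa check from every 8 hours to every 6 hours.
2. In Section 11, replace the sentence with what is shared, for example: *Trial patients receive regional citrate with a circuit iCa target of 0.25 to 0.40 mmol/L, checked hourly until in target and every 6 hours after that; the infusion regimen follows each site's protocol.* Do not claim that the regimen is identical to the registry's.
3. Carry out the match on form of anticoagulant that Section 11 already plans by using registry controls treated with regional citrate.
4. Report the citrate and calcium infusion rates that Section 6.4 already collects.

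Rewording is simpler than making Appendix K mandatory, because item 2 of that appendix prescribes CVVHDF while the trial also allows CVVH and CVVHD.

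The cost is one number, one sentence, a line on controls and one descriptive table from existing data. The downside is a weaker comparability claim and possibly fewer eligible registry controls.

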5.2 INCLUSION CRITERIA

1. A patient, or legal representative, has signed a written informed consent form.
2. Must be receiving medical care in an intensive care unit (e.g., ICU, PICU, CICU, Trauma).
3. Age less than 22 years.
4. Females of child bearing potential who are not pregnant (confirmed by a negative serum pregnancy test) and not lactating if recently post-partum.
5. Intent to deliver full supportive care through aggressive management utilizing all available therapies for a minimum of 96 hours.

6. Clinical diagnosis of AKI due to etiologies requiring CRRT (see Appendix B). AKI is defined as acute kidney injury with any one of the following:
 - Increase in SCr by ≥ 0.3 mg/dL (≥ 26.5 μ mol/L) within 48 hours or;
 - Increase in SCr to ≥ 1.5 times baseline, which is known or presumed to have occurred within the prior 7 days or;
 - Urine volume <0.5 ml/kg/h for 6 hours
7. At least one non-renal organ failure (defined as receiving mechanical ventilation or at least one vasoactive medication to treat hypotension) OR presence (proven or suspected) of sepsis (**Appendix C**).

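### Section 11 matches registry controls on listed factors but never applies the trial's eligibility criteria to them, so controls can include children the trial would have refused

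*Combined protocol and SAP*

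**What the plan says.** Eligibility (Sections 5.2 and 5.3) contains several criteria that turn on prognosis or on a clinician's decision:

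- Inclusion 5: "Intent to deliver full supportive care through aggressive management utilizing all available therapies for a minimum of 96 hours".
- Exclusion 2: "Irreversible brain damage based on available historical and clinical information".
- Exclusion 13: a current resuscitation or care limitation, including "withdrawal of care status, or anticipated change in status within the next 7 days".
- Exclusion 14: "Patient not expected to survive 28 days because of an irreversible medical condition". It extends to conditions for which the investigator regards therapy as futile.
- Exclusion 15: "Any medical condition that the Investigator thinks may interfere with the study objectives". Exclusion 16 is refusal by the physician.

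Section 11 then describes the historical comparison. It will "utilize the ppCRRT Registry to match for: etiology of AKI, co-morbidities, CRRT modality, dose and form of anticoagulant, adverse events", with "co-morbidities which will be matched for primary organ system involvement". Age, size and PRISM II score are added as matching variables. A further list of control factors covers gender, cause of AKI, total treatment duration, modality, clearance, baseline estimated GFR, urine output, fluid overload, number of vasoactive medications and mean airway pressure. From the registry's fields on the reason for CRRT, co-morbidity, modality and anticoagulation, the section concludes: "Thus, the ppCRRT Registry dataset will be able to be matched to our study patient cohort".

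No section says that the inclusion and exclusion criteria will be applied to registry records.

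**The concern.** Matching balances the variables that are matched on. It does not make controls eligible. If the treated children passed a screen for expected survival and intent of full care and the controls did not, the two groups can differ in mortality even when the device does nothing.

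The comparison has real weight in this plan. It appears in the primary objective (Section 3.1), in the synopsis secondary objective and evaluation plan, and in the DSMB's efficacy evaluation (Section 10). Section 11 says the results will guide the design of a pivotal study. A control mortality that is too high would carry over into the effect size assumed there.

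The protocol's own history shows that an external benchmark can miss. Section 2.5.3 reports that mortality in the concurrent SCD-003 control arm was about 10% below the published 45-50%. That does not show that eligibility screening was the cause.

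**Working it through.** The plan states no bias allowance, power or test for this comparison, so there is no figure of its own to reproduce. The check has two parts.

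**1. Criteria set against the Section 11 factors**

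| Criterion | Nearest listed factor | Covered? |
|---|---|---|
| Inclusion 5, full support for 96 h | none | no |
| Exclusion 13, care limitation now or anticipated | none | no |
| Exclusion 14, expected 28-day death or futility | none | no |
| Exclusions 15-16, investigator discretion, physician refusal | none | no |
| Exclusion 2, irreversible brain damage | PRISM II coma score and pupils (Appendix A) | in part: acute signs, not irreversibility |
| Exclusion 1, low blood pressure pair | PRISM II systolic pressure, vasoactive number | in part |
| Exclusions 3, 9, 12 (transplant, metastatic cancer, liver failure) | co-morbidity by organ system; PRISM II bilirubin | in part |
| Exclusions 5, 6, 17 (advanced CKD, AKI setting, weight) | baseline eGFR, cause of AKI, size | largely or in part |
| Inclusions 6-7 (AKI; organ failure or sepsis) | cause of AKI, vasoactive number, airway pressure | in part |

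**2. Illustrative size**

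Inputs:

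- p, mortality in the unfiltered controls. Section 11 gives 65% survival, hence 35% mortality, for the 201 of 370 registry children on CRRT for 1 to 7 days. This is a subgroup, neither the whole registry nor a matched set.
- f, the share of control patients who would fail the trial's screen. Not in the documents; assumed 5%, 10% and, as a stress case, 20%.
- m, mortality among those children. Not in the documents; assumed 80% and 90%.

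Mortality among eligible controls is p_e = (p − f·m)/(1 − f). The bias is p − p_e = f(m − p)/(1 − f). The share of control deaths that fall in ineligible children is f·m/p.

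| f | m | p_e | Bias (points) | Share of control deaths |
|---|---|---|---|---|
| 5% | 80% | (0.35 − 0.040)/0.95 = 32.6% | 2.4 | 0.040/0.35 = 11% |
| 5% | 90% | (0.35 − 0.045)/0.95 = 32.1% | 2.9 | 0.045/0.35 = 13% |
| 10% | 80% | (0.35 − 0.080)/0.90 = 30.0% | 5.0 | 0.080/0.35 = 23% |
| 10% | 90% | (0.35 − 0.090)/0.90 = 28.9% | 6.1 | 0.090/0.35 = 26% |
| 20% | 80% | (0.35 − 0.160)/0.80 = 23.8% | 11.3 | 0.160/0.35 = 46% |
| 20% | 90% | (0.35 − 0.180)/0.80 = 21.3% | 13.8 | 0.180/0.35 = 51% |

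With p = 50%, the upper figure in Section 1.1, the same f and m give 1.6 to 4.4 points for f = 5-10% and 7.5 to 10.0 points for f = 20%.

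For scale, Section 10 refers to 16 patients at the efficacy evaluation. A bias of 2.4 to 6.1 points is then 16 × 0.024 = 0.4 to 16 × 0.061 = 1.0 expected deaths.

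The sign follows from m − p. Removing ineligible controls who die more often than average (m > p) lowers control mortality. Removing those who die less often (m < p) raises it.

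**The case against.** Four points can be made for the plan.

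- **The net direction is not established.** A reader might infer that the bias can only favour the device. The documents do not support that. Section 11 describes the registry as recording the primary reason for CRRT, AKI among others, so it may hold children who fail inclusion 6 or 7. If they die less often, m < p for them and the bias runs the other way. This stands. The pro-device direction can be claimed only for the prognosis-based criteria.
- **Some exclusions are partly covered.** A reader might infer that matching ignores the exclusions altogether. It does not, as the table shows. The second factor list is also introduced as non-exhaustive. In addition, treatment duration is a control factor and trial patients need at least 72 hours of SCD to enter the outcome analysis, so matching on duration would tend to drop controls whose CRRT ended early through death or withdrawal. This stands too, but it leaves inclusion 5 and exclusions 13-16 without any listed counterpart at the time of selection.
- **The registry's entry rules are unknown.** A reader might infer that the controls do include children the trial would have refused. The documents give neither the registry's entry criteria nor the number of such children. Only *can include* is supportable.
- **This is a pilot.** Section 11 says the study is neither designed to assess efficacy nor powered. That lowers the stakes but does not answer the point: the issue is bias, which a disclaimer about power leaves untouched, and the comparison is still to be made and used.

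**Conclusion.** The concern holds in a limited form. The plan selects treated children on prognosis and clinician judgement and does not put the controls through the same screen. No listed factor captures inclusion 5 or exclusions 13-16, and exclusion 2 is only partly covered by PRISM II. For these prognosis-based criteria, the omission would raise control mortality and favour SCD. The net effect over all criteria is unknown in sign and size.

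The figure of about 2 to 6 points is an illustration. It rests on the 35% mortality of the 1-7 day subgroup and on assumed values of 5-10% ineligible with 80-90% mortality. The 11 to 14 points at 20% are a stress case, since about half of all control deaths would have to be in ineligible children. They should not be read as an estimate.

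The plan should be changed, but the point affects how the historical comparison is interpreted and used for planning. It does not affect the safety evaluation or any formal test.

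**What to change.** In Section 11:

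1. State that all inclusion and exclusion criteria ascertainable in the registry are applied to registry records before matching. From the fields Section 11 names, age, size, baseline eGFR, cause of AKI and parts of inclusion 7 and of the co-morbidity exclusions look feasible. The registry's data dictionary should confirm this.
2. Report the number of registry children removed at each step.
3. List the criteria that cannot be ascertained. Expected 28-day survival, anticipated care limitation and physician refusal are likely candidates.
4. For those, prespecify a sensitivity analysis that removes a stated share of control *patients* (for example 5-20%) at a stated mortality, using the formula above.

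The sensitivity analysis should be defined on patients, not on deaths. Removing 5% or 20% of control deaths gives only (0.35 − 0.0175)/(1 − 0.0175) = 33.8% or (0.35 − 0.07)/(1 − 0.07) = 30.1%, shifts of 1.2 and 4.9 points, which would not span the range being examined. The trial's screening log (Section 6.1) cannot set the bound by itself: it describes the trial sites rather than the registry, and the section does not say that reasons for exclusion are recorded.

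The cost is a smaller control pool and a little more analysis work. No trial procedure changes.
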